# Study procedure:

- The neonate's skin colour will be assessed as per the Neomar neonatal skin colour scale and categorised into one of four groups. We recognise that babies may be naturally lighter or darker than those depicted in the skin tone tool groups. When this is the case, babies will be assigned to the group closest to their natural skin colour e.g. for a baby who has a skin colour darker than group 4, they will be included within group 4.
- Additional data will be collected at two timepoints: enrollment and 14-days
- A full list of data collected including the data source and timepoints can be found in Table 1.
- Parents will be given the option to complete a web-based survey about their understanding of jaundice in neonates and its management and the impact of skin tone and/or ethnicity on jaundice assessment in neonates.

#### Procedure for collecting data:

#### Skin colour assessment:

- The skin colour assessment will be performed in a well-lit room as per skin tone tool recommendations
- The neonate will be undressed ideally fully, or at a minimum down to the nappy depending on parental preference.

#### Other clinical data:

- The remaining data (Table 1) will be collected from paper or electronic patient records, or on direct questioning of parent/carer and entered into our CRF
- The only data point collected pertaining to the second parent will be their ethnicity, which will not be identifiable. This is routinely collected as part of the infant's medical history. If the birthing parent or second parent agrees to share this on questioning, it will be included.

### Survey data:

 Within the participant information sheet, a QR code and written link will be provided for parents to access and fill in the web-based survey.

#### Focus groups and semi-structured interviews:

- The option to attend a parent and carer focus group or semi-structured interview to further explore parental perceptions and experiences of jaundice assessment will be signposted within the information sheet and at the end of the above survey.
- Parents / carers who are interested will be contacted via email. Travel, childcare and time costs will be reimbursed as per QMUL guidelines.

#### **Laboratory assessments:**

No additional laboratory assessments will be carried out on participating neonates by the research team. SBR measurements will only be done by the normal clinical team as part of routine clinical care.

#### Participant withdrawal:

Participants may withdraw from any section of the study without reason up to 1 month after data collection. Local data collectors will be able to remove the corresponding data from the study database. A replacement participant will be sought at that site if prospective data collection is still ongoing at that site at the time of withdrawal.

At the end of the survey participants will be prompted to retain the initials they used and the date they submitted their responses, if they would like to remove their data at a later date, in order for us to identify their response and remove it from the database,

#### **End of Study Definition:**

The end of the study will be the date of the last visit of the last participant in the study.

### 10. Statistical considerations

### 10.1. Sample size

We provide two sample size calculations for the two different methods used to address the Primary Objectives: linear mixed effects models (Objective 1) and Bland-Altman (Objective 2).

#### **Primary Objective 1**

We will be using a linear mixed effects model, where the confounders will be adjusted for as fixed effects, and hospitals will be fitted as a random effect. Due to the complexity of the model we will be using, the optimal method of calculating the sample size requirement *a priori* is with simulation, using *simr* in R^12. We use the following simulated dataset:

[figure not shown]
- Exposure Our exposure, skin tone, will be on 4 levels, with 1 being the lightest and 4 the darkest. No recent research on skin tone within London has been found, therefore we refer to the latest UK census results for ethnicity. For a conservative estimate, we will simulate the data for ethnicity that we would expect in London to act as a proxy for skin tone, as with the 6 categories of ethnicity (White (53.8%), Black (13.5%), Asian (20.7%), Mixed (5.7%) and Other (6.3%)). Therefore we simulate data with probability 50%, 20%, 20% and 10% for tones 1,2,3 and 4, respectively.
- We assume that we will have 20 hospitals collecting data, therefore we have 20 clusters to be a random effect
- The outcome will be simulated depending on skin tone and age. Age will be uniformly distributed between ages 0 and 96 hours. Bilirubin mean will be simulated according to the following formula:
  - Bilirubin (μmol/L)=2.6\*age (hours)+60+20\*skin tone+60 with standard deviation 10. The coefficient and intercept, 2.6 and 60 respectively, is to fit the line where babies begin to need phototherapy according to the NICE jaundice treatment threshold graphs.

We wish to achieve an effect size of 10 µmol/L for skintone 2 compared to skin tone 1, 20 µmol/L for skin tone 3 compared to skin tone 1, and 30 µmol/L for skintone 4

compared to 1. We perform 100 simulations for each simulated cluster size (between cluster sizes of 10 and 50 neonates), and estimate the average power achieved. Assuming a 95% confidence interval (CI), we can plot the number in each cluster against the estimated power.

If we were to assume a power of 80% at minimum, we would require each hospital to contribute at least 28 participants (power is 78% at 27 participants and power is 80% at 28 participants). However, estimating *a priori* is making strong assumptions on the data and we have not accounted for missing data. We recommend that once the study has recruited a minimum of 10 participants in each cluster (hospital), monthly updated target study sample sizes are to be calculated based on the data accumulated so far.

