Following initial sample size calculations (detailed in Section 10) it has been estimated that a total of 560 participants will need to be recruited, to adequately power the study's Primary Objectives 1 and 2. Therefore, we will aim to recruit a

minimum of 28 participants at each site. An initial recruitment window will aim to recruit 10 participants per site. If there is insufficient recruitment to particular skin tone groups, recruitment windows can be reopened in centres where recruitment of participants of that group is most likely.

Data collection periods may need to be staggered according to the timings of individual Trust R&D approval processes. The total anticipated time for the study is currently 18 months, of which approximately the first 9 months will include local site approval processes and data collection, followed by a 9 month period of analysis and preparation for dissemination (see Gantt chart attached for further detail).

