## 10.2. Method of analysis

Due to the *a priori* nature of the sample size calculations, these will be redone based on interim data. This is suggested once each hospital has at least 10 participants. Then a readjustment shall be done every two-three months until sample size has been reached for both primary objectives. This will include the use of bilirubin measures, skin tone and age at TcB measurement, but no other data. The statistician will provide the study leads with the updated targets with no other interim analysis. This may reduce or extend study length depending on the targets of both primary objectives.

Data will be analysed on exposure in accordance with the allocation on skin colour scale. We expect limited missing data. If missing data is <5% for any covariate then analysis will be restricted to complete case analysis. Multiple imputation will only be used if missing data is >5% for any category.

All data collated will be presented in summary tables, stratified by skin colour. Continuous data will be summarised in terms of the mean, standard deviation (SD), median, minimum, maximum and number of observations, when the data are approximately normally distributed.. Continuous data that are expected to be skewed will be presented in terms of the maximum, upper quartile, median, lower quartile, minimum and number of observations. The minimum and maximum will be reported to the same number of decimal places as the raw data recorded in the database. The mean, median, lower quartile and upper quartile will be reported to one more decimal place than the raw data recorded in the database. The SD will be reported to two more decimal places than the raw data recorded in the database. In general, the maximum number of decimal places reported shall be four for any summary statistic. Categorical data will be summarised in terms of the number of participants providing data at the relevant time point (n), frequency counts and percentages. The number of participants with missing information for a specific variable will be displayed if applicable. Any planned collapsing of categories will be detailed in the SAP text and the data displays. Percentages will be presented to one decimal place. Percentages will not be presented for zero counts. Percentages will be calculated using non-missing data as the denominator. Confidence intervals (CI) will be presented to one more decimal place than the raw data.

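### The 28-per-hospital target rests on a step from 78% to 80% power estimated with 100 simulations per size, too few to tell 27 from 28, and the inputs behind the 80% need reconciling before any re-run

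*Protocol*

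**What the plan says.** Protocol section 10.1, Primary Objective 1, plans a linear mixed model with hospital as a random effect and obtains power by simulation. The number of runs is stated: "We perform 100 simulations for each simulated cluster size (between cluster sizes of 10 and 50 neonates), and estimate the average power achieved". The chosen size follows from two adjacent points on the resulting curve: "If we were to assume a power of 80% at minimum, we would require each hospital to contribute at least 28 participants", supported by "power is 78% at 27 participants and power is 80% at 28 participants". With the assumption "We assume that we will have 20 hospitals collecting data", this becomes the figure in section 8: "a total of 560 participants will need to be recruited".

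Section 10.1 concedes that the calculation makes strong assumptions and allows nothing for missing data. It does not mention simulation error, and the readable text gives no interval for the 78% or the 80%. Section 10.2 then says of the sample size calculations that "these will be redone based on interim data", and that the updated targets may shorten or lengthen the study. No replicate number is given for those later runs.

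**The concern.** Power estimated by simulation is a proportion with its own sampling error. Here a two-point difference between neighbouring cluster sizes decides the target, yet each of the two estimates carries an error several times that size. The printed 80% is therefore less firm than it looks, and the choice of 28 over 27, or over sizes a little further away, is partly chance.

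The planning figure is also meant to be recalculated during recruitment. If each recalculation used 100 runs, the target could move by several infants per hospital with no change in the accumulating data, and recruitment is to continue until the current target is met.

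**Working it through.** **Inputs** (Protocol section 10.1): 100 simulations per cluster size; power 78% at 27 and 80% at 28; 20 hospitals; SD 10 µmol/L; target effects of 10, 20 and 30 µmol/L for tones 2, 3 and 4 against tone 1; shares 50/20/20/10%. The stated 95% confidence level is taken as two-sided alpha 0.05. The between-hospital variance is not printed.

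**1. The plan's own figures.** The total is right: 20 × 28 = 560. The 80% does not reproduce. For the weakest contrast (tone 2 against tone 1) at N = 560:
- group sizes 0.5 × 560 = 280 and 0.2 × 560 = 112
- standard error = 10 × √(1/280 + 1/112) = 1.118
- power = Φ(10/1.118 − 1.96) = Φ(6.98), above 99.9%

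At 10 per hospital (groups of 100 and 40) the standard error is 1.871 and power is Φ(5.35 − 1.96) = 99.96%. The other two contrasts are stronger. A simulation with 20 hospitals, age as a covariate and an assumed between-hospital SD of 10 agreed: 99.75% for the weakest contrast at 10 per hospital and 100% at 28 (400 runs each). Power of 80% for the 10 µmol/L contrast would need a residual SD of about 10/(2.80 × 0.1118) = 32. In addition, the generating formula adds 20 per tone step while the target effects rise by 10 per step.

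**2. Monte Carlo error, if the power is a single-test proportion of 100 runs.**
- At 28: SE = √(0.80 × 0.20/100) = 4.0 points; 95% half-width 7.8; exact (Clopper-Pearson) interval 70.8% to 87.3%.
- At 27: SE = √(0.78 × 0.22/100) = 4.1 points; exact interval 68.6% to 85.7%.
- Step, with independent runs: SE = √(0.001716 + 0.0016) = 5.8 points; z = 2/5.8 = 0.35.
- If true power were 78% and 80%, the estimate at 27 would equal or exceed that at 28 in about 40% of repeats.

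**3. Illustration of the effect on the target.** Two assumptions that are not in the Protocol: true power at size k is Φ(2.80 × √(k/28) − 1.96), which is 80% at 28; and the target is the first size from 10 to 50 whose estimate reaches 80%.
- 100 replicates: selected size 23 to 30 in 95% of 20,000 repeats (20 × 23 = 460 to 20 × 30 = 600 infants); mean true power at the selected size 77.5%. The rule stops early on average because it takes the first lucky draw.
- 2,000 replicates: 27 to 29 in about 97% of repeats, mean true power about 80.5%.

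**4. Replicates needed.** At 80% power, 2,000 replicates give SE = √(0.16/2000) = 0.9 points. A 95% half-width of 2 points needs 1.96² × 0.16/0.02² ≈ 1,540 replicates; 1 point needs about 6,150. Resolving the difference between two neighbouring sizes to within 2 points takes about 3,200 per size, which is why a fitted curve is better than a comparison of neighbours.

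**The case against.** Several objections have force.

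- *The 80% may not be 80 successes in 100.* Section 10.1 lists three contrasts and then speaks of average power. An average over contrasts would have a smaller error. This stands as a limit on the interval, but it does not rescue the step. Suppose the contrasts were independent and two had power of 100%, so that averages of 80% and 78% imply 40% and 34% for the third. The SE of the step is then √((0.40 × 0.60 + 0.34 × 0.66)/900) = 2.3 points, against a step of 2.
- *Runs at different sizes may share random draws.* That would sharpen the comparison of 27 with 28. It would not reduce the 4-point error in the level at either size, so which one truly reaches 80% would stay unknown.
- *The whole curve carries more information than one point.* This stands. From the 80/100 alone one might infer a range of about 23 to 35 per hospital (460 to 700 infants). That discards the rest of the curve and relies on an assumed shape, so it should not be quoted as the uncertainty in the target.
- *An interval may already be shown.* The sentence "Assuming a 95% confidence interval (CI), we can plot the number in each cluster against the estimated power" could refer to alpha or to an interval on the plot, and a figure in that section is not available. The point therefore concerns how 28 was chosen; it is not a claim that no interval was ever computed.
- *The target is provisional.* It is, and re-estimation can correct wrong inputs. It cannot remove noise that it would itself regenerate. A reader might infer that the re-estimated targets are unreliable as planned. The Protocol does not support that, because it states no replicate number for them and the analysis plan may.

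**Conclusion.** The point holds as a minor one about simulation precision. There is no multiplication error. With 100 runs per size, 27 and 28 per hospital cannot be distinguished, and a single-test power of 80% is known only to within about 8 points. The 23-to-30 range and the mean true power of 77.5% are illustrations that rest on the assumed curve and first-crossing rule. The carry-over to interim targets depends on 100 runs being kept.

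Two stronger inferences are tempting and not supported. One is that 560 is too few: first-crossing selection errs towards low power, but the printed inputs point the other way, to power near 100%. The other is that 80% is right apart from simulation noise: noise of 4 points cannot explain a gap between 80% and more than 99.9%. The mismatch in inputs is the larger problem, and more replicates alone would not make the 80% reliable.

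**What to change.** In this order:

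1. Reconcile and print the simulation inputs: residual SD, between-hospital variance, effect per tone step (20 in the formula, 10 in the targets) and which test or average the power refers to. Confirm that they generate the reported curve.
2. Re-run with at least 2,000 replicates per cluster size, fit a smooth monotone curve of power against size, and read the target from it.
3. Report the power at the target with its Monte Carlo interval.
4. State in section 10.2 that each re-estimation uses the same number of replicates and the same reading rule.

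Until step 1 is done, do not print the power as about 80% with an interval of 71% to 87%. That would put a simulation interval around a figure the stated inputs contradict.

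The computing takes a few hours and the text changes are short. The real cost is that the stated power and the target of 28 per hospital may change materially.

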Primary objective 1 will be using a linear mixed model, with skin tone and confounders as fixed effects and hospital as a random effect. The outcomes will be the coefficient difference between baseline skin tone and the other 3, with 95% CI.

Primary objective 2 will use the Bland-Altman to detect differences of measurement between skin tones, stratified by method of how the measurement for how serum bilirubin was taken. The mean of the differences will be provided with 95% CI, along with the IQR of difference with accompanying p-value. The rate of over/under-estimation will also be estimated between different skin tones. Bland-Altman plots will be reported as well as Specificity and sensitivity analyses using Receiver operating characteristic (ROC) curves.

Secondary Objective 1: Primary length of admission differences between skin tone will be compared using survival analysis of time to event data (Kaplan-Meier plot, Cox Proportional Hazards Model). The need for interventions including phototherapy and exchange transfusion will be done using generalised linear mixed models, with outcomes reported as Odds Ratios with 95% CI.

Age of infant at measurement is an important metric and shall be included as a fixed covariate in all models other than Bland-Altman (baseline model). Additionally, IMD and gestational age may be included as additional covariates (adjusted model). However, due to the complex relationship between skin colour and medical intervention, we run the risk of over-adjusting on covariates and inducing collider bias and/or mediators. For example, skin tone may affect what the indication for jaundice assessment was, and this in turn may affect the outcome of bilirubin and if there was a delay for treatment, making it a mediator. With sufficient time, this relationship may be explored to see if different skin tones are affected by how their jaundice is first indicated, which influences clinical guidelines if an association is found between skin tone and indication which in turn affects bilirubin levels.

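### The 80% power stated for Primary Objective 1 does not follow from the stated simulation inputs and the planned age-adjusted model

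*Protocol*

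**What the plan says.** Protocol section 10.1 (Primary Objective 1) describes a simulated dataset with these features:

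- **Hospitals:** "We assume that we will have 20 hospitals collecting data", with hospital as a random effect.
- **Skin tone:** tones 1 to 4 drawn with probabilities 50%, 20%, 20% and 10%.
- **Age:** uniform from 0 to 96 hours.
- **Bilirubin:** mean equal to 2.6 times age in hours, plus 60, plus 20 times "skin tone+60 with standard deviation 10".
- **Targets:** "We wish to achieve an effect size of 10" µmol/L for tone 2 against tone 1, then 20 for tone 3 and 30 for tone 4.
- **Runs and error rate:** "We perform 100 simulations for each simulated cluster size (between cluster sizes of 10 and 50 neonates"), with "Assuming a 95% confidence interval (CI"), which I read as a two-sided 5% level.

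The result opens with "If we were to assume a power of 80% at minimum" and concludes that 28 per hospital are needed, because "power is 78% at 27 participants and power is 80% at 28 participants". Section 8 carries the resulting 560 forward as the number that adequately powers both primary objectives.

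Section 10.2 fixes the analysis as a linear mixed model. The reported outcomes are the three differences from the baseline tone, each with a 95% CI. It also says: "Age of infant at measurement is an important metric and shall be included as a fixed covariate in all models other than Bland-Altman".

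**The concern.** Three things do not fit together.

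1. The formula and the targets describe different effects. A coefficient of 20 per tone step gives 20/40/60 against tone 1; the next paragraph wants 10/20/30. The formula also contains 60 twice, although the text explains a single intercept of 60. The second 60 does not affect power, but it shows that the formula was not checked against its explanation.
2. An SD of 10 is very small beside effects of 10 to 60 in several hundred infants. Once age is fitted, power should be close to 100% well before 28 per hospital.
3. Three coefficients are to be reported, but one power is given, and neither a contrast nor a joint test is named.

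560 is the study's headline number. If the 80% belongs to a model that will not be fitted, it says nothing about the planned analysis, and the scheduled recalculations could inherit the same set-up.

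**Working it through.** **Inputs.** From section 10.1: 20 hospitals; tones 50/20/20/10%; age uniform 0–96 h; slope 2.6; SD 10; effects 10/20/30 (targets) or 20/40/60 (formula); two-sided 5%. From section 10.2: age in the model, three contrasts against tone 1.

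For a contrast δ, SE = SD × √(1/n₁ + 1/nₖ) and power ≈ Φ(δ/SE − 1.96). The simulation draws age without regard to tone, so fitting age changes the SD but not the square-root factor. Tone varies within hospitals, so a random intercept barely changes these contrasts.

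| N (per hospital) | Tones 1/2/3/4 | Factor, tone 2 or 3 vs 1 | Factor, tone 4 vs 1 |
|---|---|---|---|
| 200 (10) | 100/40/40/20 | 0.1871 | 0.2449 |
| 540 (27) | 270/108/108/54 | 0.1139 | 0.1491 |
| 560 (28) | 280/112/112/56 | 0.1118 | 0.1464 |

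**1. Stated inputs with the planned model (age fitted, SD 10).** Take the smallest cluster size and the smaller effects. At N = 200, tone 2: SE = 10 × 0.1871 = 1.871, δ/SE = 5.34, power = Φ(3.38) = 99.96%. Tones 3 and 4 have δ/SE of 10.7 and 12.2, so power is effectively 100%. Larger clusters or the 20/40/60 effects only raise these figures. The printed 78% and 80% are not reproduced, and power cannot cross 80% anywhere between 10 and 50 per hospital.

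**2. What comes close: age left out.** Age then adds an SD of 2.6 × 96/√12 = 72.05, and the total SD is √(72.05² + 10²) = 72.74. With effects 10/20/30 at N = 560:

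- tone 2: SE = 72.74 × 0.1118 = 8.13; 10/8.13 = 1.23; power 23.3%
- tone 3: 20/8.13 = 2.46; power 69.1%
- tone 4: SE = 72.74 × 0.1464 = 10.65; 30/10.65 = 2.82; power 80.4%

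At N = 540, tone 4 has SE 10.84 and power 79.0%. A random-intercept simulation without age (200 runs, assumed hospital SD 10) gave 78.5% for tone 4 at 28 per hospital.

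For the joint 3-df test, the mean effect is 0.2×10 + 0.2×20 + 0.1×30 = 9 and the between-tone variance is 20 + 80 + 90 − 81 = 109. So λ = 560 × 109/72.74² = 11.5, and power is 82.1% (80.6% at N = 540).

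With the formula's 20/40/60 and age omitted, power at 560 is 69.1%, 99.8% and about 100%; no single contrast gives 80%.

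**3. The printed pair does not identify the run.** If the SD were not 10 but about 32, the age-adjusted tone 2 contrast would give 10/(32 × 0.1118) = 2.80, power 79.8% at 28 and 78.4% at 27.

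**4. Simulation error.** The exact 95% interval for 80 successes in 100 runs is 70.8% to 87.3%. A two-point step between 27 and 28 lies inside the noise.

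**5. Dependence on the residual SD.** The table under Primary Objective 2 gives group SDs of 34 to 43, with no stated age adjustment. Used as a pessimistic bracket at N = 560 with effects 10/20/30:

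| SD | Tone 2 | Tone 3 | Tone 4 |
|---|---|---|---|
| 34 | 74.9% | >99.9% | >99.9% |
| 43 | 54.8% | 98.6% | 99.7% |

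80% for tone 2 needs δ/SE = 1.96 + 0.84 = 2.80, that is SD ≤ 10/(2.80 × 0.1118) ≈ 32.

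**The case against.** The protocol can be defended on three grounds.

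- **The number is provisional.** Section 10.1 admits strong assumptions, and sections 10.1 and 10.2 schedule recalculation once each hospital has 10 participants, using bilirubin, skin tone and age. This stands as far as it goes: 560 may change. But the recalculation does not correct the printed derivation, does not name the contrast or test, and does not say that age will be in the model used for it.
- **What was run is not known.** A figure in the simulation description was not available in the text I worked from, and the printed pair fits more than one set-up. A reader might infer that age was certainly omitted and that the 80% is certainly tone 4 against tone 1. The documents do not establish that: the age-omitted joint test fits within simulation error, and so does an age-adjusted tone 2 contrast with SD about 32, which departs from the stated SD. The mismatch in step 1 does not depend on knowing which was run.
- **The SDs of 34 to 43 are not residual SDs.** They come from a prior study, and no age adjustment is stated. If bilirubin rises with age, as the simulation assumes, the age-adjusted SD would be smaller. This stands, so the bracket is pessimistic and does not show that an SD of 10 is wrong.

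**Conclusion.** The point holds as an error in the stated derivation. The formula contradicts the target effects. The stated inputs with the planned age-adjusted model give at least 99.9% power for every contrast from 10 per hospital upward, so the printed 78% and 80% cannot have come from them. Which contrast or test the 80% describes is not stated. This rests on the protocol's own inputs, a two-sided 5% level and tone varying within hospitals.

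A reader might go further and infer that the study has only 23% power for tone 2 and 69% for tone 3. The documents do not support that. Those figures belong to a model without age, which section 10.2 rules out. Power in the planned analysis depends on an age-adjusted SD that the protocol does not justify: close to 100% throughout if it is 10, and below 80% for tone 2 alone if it lies between about 32 and 43. The finding is that 560 has no valid stated basis for Objective 1, not that 560 is too few.

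**What to change.** In section 10.1:

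1. Make the formula and the target effects agree, and remove or explain the second 60.
2. Re-simulate the mixed model that will be fitted, with age as a fixed effect and hospital as a random effect. State the hospital variance assumed, and use more runs (for example 1,000, for which the Monte Carlo SE at 80% is √(0.8 × 0.2/1,000) = 1.3 points instead of 4).
3. Justify the age-adjusted residual SD. Until interim data exist, show power over a range, with 34–43 labelled as an unadjusted, pessimistic bracket.
4. Replace the single 80% with power at 560 for each of the three contrasts. A trend test across the ordered tones could be added but is optional.

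In section 10.2, state that the recalculation uses the same age-adjusted model and name the contrast or test that sets the target.

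The cost is a few hours of work and a rewritten paragraph. Restating power needs no extra infants, but the figure for tone 2 may be less favourable. If the sponsor then wanted 80% for tone 2 at the pessimistic SDs, N = 7 × SD² × 2.80²/10² gives roughly 640 (SD 34) to 1,020 (SD 43) infants, where 7 = 1/0.5 + 1/0.2. That would be a separate decision.
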